in a 12HR combination since both isoniazid and rifapentine can damage the liver; CDC is calling for studies of 12HR in prisoners, but have not yet funded research. In the absence of studies of 12HR use in prisoners, it is crucial to assess both completion rates and tolerability (especially when high HCV prevalence is present).

Eligibility for Part B includes:

- 1) Meets inclusion criteria for Part A
- 2) Has latent TB (HIV+, or TST \geq 10mm (HIV-)) and no active TB disease
- 3) \geq 6 months before end of sentence to ensure option for treatment completion
- 4) AST/ALT <5 ULN, or AST/ALT <3 x ULN if TBil >2 x ULN
- 5) Not on a protease inhibitor (drug interaction with rifapentine)
- 6) No known porphyria
- 7) Not pregnant (women only).

Enrolled participants will undergo block stratified randomization, stratifying on four factors: a) CD4 <350 (if HIV+); b) HCV Ab status; c) ART status; and d) opioid dependence. After randomization and allocation to 12HR or 26H, participants will be provided 12HR weekly (12 weeks) and 26H daily (26 weeks) as directly observed therapy. Every 4 weeks, patients will be monitored for AST/ALT, adverse side effects and pregnancy. Premature treatment discontinuation will occur for any DAIDS Grade 4 toxicity, patient refusal to continue, or pregnancy (women only).

Study Design: TB Studies

Legend: LTBI=latent TB infection; H=isoniazid; HP=isoniazid + rifapentine; MMT= methadone maintenance treatment; BPN/NLX= buprenorphine/naloxone; OAT=opioid agonist treatment; ART= antiretroviral therapy; HCV= hepatitis C virus.

Part C:

A two-arm **preference trial** (no MAT, and methadone) of prisoners with opioid use disorders who are not or are currently being treated for TB and/or HIV, and are about to transition to the community and need to continue their treatment post-release. Patients may or may not be returning to Klang Valley and within 25 km of our research site. We anticipate enrolling 25-50 participants per arm.

Once consented, study participants will be provided an informed decision-making aid that will help them decide if medication-assisted treatment, specifically Methadone, is best for them. Participants will also have the option not to enroll in medication-assisted treatment.

[figure not shown]
Informed decision-making aid:

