For patients in Aim 1, Part B (trial of 26H vs 12HR) and Part C (MMT, vs. no MAT), patients will be seen monthly clinically for symptoms of hepatitis or neuropathy and LFTs shall be monitored. Anyone whose LFTs increase to $>5X$ ULN, or $>3X$ ULN with symptoms of jaundice, nausea or fatigue, will be stopped from receiving medications and LFTs will be monitored weekly to ensure that LFTs are decreasing. Similarly, if patients develop Grade 3 or higher peripheral neuropathy, they will be discontinued. Of note, LFTs will be measured at baseline and monthly for 3 months for 12HR and monthly x 6 months for 26H.

MMT patients will be seen daily for the first month and may have their medications dispensed less frequently if they have no evidence of using illicit drugs by self-report or urine testing.

11. Data and Safety Monitoring Plan: Include an appropriate Data and Safety Monitoring Plan (DSMP) based on the investigator's risk assessment stated below. (Note: the HIC will make the final determination of the risk to subjects.) For more information, see the Instructions, page 24.

- a. What is the investigator's assessment of the overall risk level for subjects participating in this study?
- b. If children are involved, what is the investigator's assessment of the overall risk level for the children participating in this study?
- c. Include an appropriate Data and Safety Monitoring Plan. Examples of DSMPs are available here <http://www.yale.edu/hrpp/forms-templates/biomedical.html> for
 - i. Minimal risk
 - ii. Greater than minimal

Aim 1parts (a-c) requires a DSMB.

Data and Safety Monitoring Board

We will comprise a full Data and Safety Monitoring Board (DSMB), that will include three voting members from colleagues in the field. The PI on this grant is familiar with the implementation of a DSMB; he is currently serving as one of the board members of the NIDA Clinical Trials Network studies examining routine HIV testing among drug users.

The key elements of a DSMB include the following:

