- 1) Selecting experts in the field (HIV, TB, Substance abuse) who will serve as members of the board. If funded, we will select two U.S. and one Malaysian experts to serve on the DSMB. As in other NIDA trials, we will work with NIDA staff to select these individuals. Individuals from NIDA will be responsible for the final invitation to participate on the Board. During the first six months of the study, while final implementation is being conducted, the DSMB will convene to go over their charge, examine the guidance set forth by the study team and to question the PI and biostatisticians about pre-defined endpoints. Once these outcomes and stopping rules are defined, the Board will reconvene at regularly scheduled times to assess outcomes.

Defining stopping rules. For Aim 1, part B, we will be examining completion and tolerability of two LTBI prevention strategies. The study is not powered to reduce development of active TB, but to establish safety in prisoners who have high prevalence of HCV infection. Tolerability (discontinuation from study medication) will be the primary outcome. All discontinuations will be reviewed by the PI and the team. Death will be brought to the DSMB within 24 hours if medication related (though most deaths are related to TB itself). If the discontinuation rate is 3-fold higher in either group, either in the interim analysis when 50% is enrolled or at any time within study assessment, the study will be stopped for safety purposes and a press release will be made. For Part B, we anticipate a difference between the control group and the two intervention groups of about 40%.

- 2)
- 3) Assessment of possible adverse consequences of the various interventions. No specific guidance is available for DSMBs for these kinds of interventions; however, we have considerable experience with CHRP, Project PLUS, Project TRUST, Project CONNECT, Project BEST and other community research studies to provide a specific plan. In fact, in order to collect information about the "safety" of the intervention, we intend to hire a research assistant to gather safety information from three independent sources. These include the weekly study meeting where all active participants are discussed, daily conversations with the Health Educators and weekly conversations with the subject

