- c. Assessment of adverse consequences: Several different research staff members will assess subjects in both the MMT and IPT interventions. For those on MMT who receive either HAART or TB Treatment, we will monitor for symptoms of opioid withdrawal. Alternatively, we will monitor for overdose in these subjects, diversion or drug interactions with MMT. We would also monitor for breaches of confidentiality in PT subjects. An initial investigation would be undertaken and simultaneously reported to the IRB using standard university procedures.
- d. Confidentiality of research data: Breaches of confidentiality regarding research data are more difficult to detect. For that reason, we have in place a number of safeguards including double-locked doors, locked file cabinets, confidential and dedicated fax machine and double password-protected computers. In accordance with federal and university policy, all research personnel are compliant with HIPAA training. If any breach of data confidentiality were detected, we would use similarly detailed procedures for report to the PI and IRB simultaneously.
- e. Complications from MMT: In this study, we will monitor for adverse consequences in a standard way. First, drug interactions between buprenorphine and HIV antiretrovirals have not been extensively evaluated. Efavirenz and nevirapine have been associated with reductions in methadone levels, and precipitated clinical withdrawal. In cases where we can detect symptoms of opiate withdrawal, we will increase the methadone dose to treat the symptoms of withdrawal. [name] was the first clinician to report cases of opiate withdrawal among patients receiving HAART and methadone and is currently investigating other pharmacokinetic interactions between methadone and buprenorphine with antiretroviral drug interactions. Methadone may

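### In the available text, the only overdose-specific monitoring rule covers methadone patients, so the no-OAT arm of Part C has only general safety capture

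*Combined protocol and SAP*

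**What the plan says.** Section V.11 (Data and Safety Monitoring Plan), item c, opens with a general statement: "Several different research staff members will assess subjects in both the MMT and IPT interventions". It continues: "For those on MMT who receive either HAART or TB Treatment, we will monitor for symptoms of opioid withdrawal". The overdose sentence follows directly: "Alternatively, we will monitor for overdose in these subjects, diversion or drug interactions with MMT". This is the only place in the available text where overdose is named.

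Item e of the same section, on complications from MMT, has a methadone nurse see patients every day and send anyone who is over-sedated to the physician. HAART or TB treatment is not a condition.

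The general safety system is in section V.11, item 3. A research assistant gathers safety information from "the weekly study meeting where all active participants are discussed", and from "daily conversations with the Health Educators and weekly conversations with the subject". The available text breaks off there and resumes at item c.

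Three other places matter:

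- **Section V.3, Part C.** It enrols "prisoners with opioid use disorders who are not or are currently being treated for TB and/or HIV", in two self-chosen arms, methadone and no MAT. On size: "We anticipate enrolling 25-50 participants per arm". Everyone is seen monthly after release for urine screening, timeline follow-back of alcohol and drug use, the short Addiction Severity Index, diversion and other items. Overdose is not listed.
- **Section V.10, Monitoring Adverse Side Effects.** For Part B and for both arms of Part C, "patients will be seen monthly clinically for symptoms of hepatitis or neuropathy and LFTs shall be monitored". Methadone patients also have daily contact during the first month.
- **Section V.7.** It foresees that some women who prefer no OAT will relapse, and lets them start methadone and stay in the study.

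**The concern.** Opioid dependence is an entry criterion for all of Part C, and everyone is followed after leaving prison. Overdose is thus a possible serious harm in both arms, and the plan treats it as serious enough to name. Yet the sentence that names it is tied to methadone. In the other arm an overdose is recorded only if someone brings it up in a general conversation, or if it surfaces during the drug-use assessment.

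Two things are at stake. The first is complete capture of a serious harm in people under study follow-up. The second is interpretation: if overdoses and deaths are later set side by side by arm, the stated monitoring differs between the arms being compared.

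**Working it through.** There is no planned figure to reproduce. The check is one of scope, followed by a head count.

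**Step 1: whom does the overdose sentence cover?** Two readings of item c are possible.

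- *Narrow:* the phrase refers to the sentence just before it, that is, methadone patients who also receive HAART or TB treatment.
- *Broad:* it reaches back to the opening sentence on the MMT and IPT interventions. Because overdose is listed beside diversion and drug interactions with MMT, the sensible broad reading is all methadone patients.

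People in the no-OAT arm are outside on both.

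**Step 2: what does each group have in the available text?**

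| Provision | Methadone arm | No-OAT arm |
|---|---|---|
| Overdose named (V.11, item c) | Yes (all, or those on HAART/TB treatment) | No |
| Sedation watch and referral (V.11, item e) | Yes | No |
| Daily contact in month one (V.10) | Yes | No |
| Monthly hepatitis, neuropathy and LFT review (V.10) | Yes; overdose not listed | Yes; overdose not listed |
| Monthly urine screen and drug-use assessment (V.3) | Yes; overdose not listed | Yes; overdose not listed |
| Weekly meeting and conversations (V.11, item 3) | Yes; not overdose-specific | Yes; not overdose-specific |

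The clear gap is the no-OAT column.

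**Step 3: how many people is that?** The input is 25-50 per arm (V.3, Part C).

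Share outside the rule = n(no OAT) / [n(no OAT) + n(methadone)]

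- Equal arms: 25/50 = 50/100 = 50%.
- Unequal arms, which are possible because participants choose: 25/(25 + 50) = 33.3%, up to 50/(50 + 25) = 66.7%.

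These are people outside a named rule, not overdoses missed. The documents give no overdose rate and no capture rate for the general system, so missed events cannot be calculated.

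**The case against.** The best case for the plan has three parts.

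**The text is incomplete.** Section V.11 breaks off in item 3 and resumes at item c, and the interview forms are not in the documents. A rule for the no-OAT arm could sit in either place. This stands as a limit: absence can be claimed only for the text available. But a broader rule elsewhere would still need to be squared with the wording of item c.

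**The rule concerns harm from the intervention.** The no-OAT arm receives no study opioid, so overdose after relapse belongs to the course of the disease, and a methadone-toxicity rule limited to methadone patients is not an error. That is fair as a reading of intent. It does not remove the case for recording a serious event in both arms of a comparison when all participants are opioid-dependent. The allowance for relapsing women to start methadone brings them under methadone monitoring only once they have started it.

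**General capture exists.** The weekly meeting discusses all active participants, conversations take place daily and weekly, and drug use is assessed monthly. None of this is visibly confined to methadone patients. This stands too, so a reader should not infer that overdoses in the no-OAT arm would go unseen. What remains is that capture depends on someone raising the event.

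A reader might also infer from the narrow reading that methadone patients without HAART or TB treatment form a second uncovered group, which would take the share outside towards the whole of Part C. The documents do not support that. The sedation watch and the early daily contact apply to methadone patients whatever their other treatment, and the share of the methadone arm without HAART or TB treatment is not given. Weekly take-away dosing does make daily observation after release doubtful, but it does so for all methadone patients alike.

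**Conclusion.** The point holds for the no-OAT arm. In the available text its 25-50 opioid-dependent participants have no overdose-specific monitoring, while the methadone arm does. That is half of Part C with equal arms and 33% to 67% if the arms differ within the planned range. The conclusion rests on two assumptions: that the unseen part of section V.11 and the interview forms hold no overdose item for this arm, and that each arm stays within 25-50.

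The consequence is modest. The primary outcome, completion of TB treatment, is unaffected, and no overdose comparison is planned. A reader might infer that one arm would look falsely safer. The documents do not support a size or a direction for such a bias: they give neither overdose risks nor capture rates by arm, and participants choose their arm. The 15-20% attrition expected in section V.12 applies to Part C as a whole and adds nothing to this point.

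This is a worthwhile, inexpensive improvement in safety capture, not a flaw that undermines the trial.

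**What to change.** 1. Reword the overdose sentence in section V.11, item c, so that overdose is monitored in every Part C participant, whichever arm is chosen and with or without TB or HIV treatment.
2. Add one defined overdose item to the existing monthly visit in both arms: any overdose since the last visit, its date, and whether it was fatal. Staff would complete the same item when they learn of a fatal event through the general safety channels.
3. Report overdoses and deaths descriptively by arm, labelled as non-randomised data.

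The cost is one sentence, one item in an interview that already takes place, and one table. No new visits or staff are needed. If the forms already ask about overdose in both arms, item 2 falls away. The downsides are a slightly longer interview and counts that will be imprecise at 25-50 per arm, so the table should not be read as a comparison of risk.

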saturation of themes is reached. Participants will undergo informed consent prior to participating, and will be compensated 50RM for their time.

Upon making an informed decision using the SDM developed from the focus groups, those that choose methadone maintenance treatment (MMT) will initiate 5 mg of methadone, 3-4 months prior to release from prison. The dose will increase in 5 mg increments every 7 days (as tolerated) until the daily dose is escalated to at least 80 mg or optimal dose before the date of release. Patients prescribed MMT will receive medication daily in prison, and will receive their medications weekly in form of take-way dosing. MMT will be dispensed at the community research site. All participants will be maintained on medication-assisted treatment and will receive follow-up care for 6 months after release from prison.

After a baseline assessment, our research assistant (RA) would meet the participant at the prison on the day of release to undergo a brief assessment, urine testing and to introduce the patient to our community research site to ensure that s/he can find the site after release and take the participant home so that our research assistants can know where the person is living/residing. This process will also improve trust between the research staff and the participant. Thereafter, all participants will be seen monthly, where they will undergo urine screening and be assessed for alcohol and drug use using timeline follow-back (TLFB), appointments for HIV and/or TB, adherence to HIV and/or TB medications, assessments of legal, employment, family issues using the Lite version of the Addiction Severity Index (ASI), depressive symptoms, health-related quality of life (HRQoL), satisfaction with their treatment. They will also be assessed for diversion (and urine testing).

The primary outcome will be the proportion completing treatment for active or LTBI. Secondary analyses will compare Kaplan Meier curves using Cox proportion hazards and time to discontinuation. TB treatment adherence will also be measured using MEMS caps and analyzed as we have done previously in TB patients in Ukraine

Eligibility for Part C includes:

- 1) Meets inclusion for part A, if possible
- 2) Opioid dependence
- 3) Has LTBI or active TB disease (based on screening in Part A), or no TB
- 4) Returning to live in Kuala Lumpur/Klang Valley region (within 25 km of Kerinchi research site), if possible
- 5) ≤ 6 months before end of sentence

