Erlotinib	Possible decreased erlotinib AUC ^b	Avoid concomitant use if possible ^b
Fluoroquinolones (e.g., ciprofloxacin)	Potential increased metabolism of ciprofloxacin ¹	Dosage adjustment of the fluoroquinolone may be needed ¹
Estrogens/Progestins	Hormonal contraceptives (oral or other systemic): Potential interaction with oral or other systemic hormonal contraceptives ¹	Use nonhormonal methods of contraception ¹
Immunosuppressive agents (cyclosporine, tacrolimus)	Potential increased metabolism of the immunosuppressive agent ¹	Dosage adjustment of the immunosuppressive agent may be needed ¹
Levothyroxine	Potential increased levothyroxine metabolism ¹	Dosage adjustment of levothyroxine may be needed ¹
Macrolides (clarithromycin)	Potential increased clarithromycin metabolism ¹	Dosage adjustment of clarithromycin may be needed ¹
Opiate agonists (methadone)	Potential increased metabolism of methadone ¹	Dosage adjustment of methadone may be needed ¹
Psychotherapeutic agents (amitriptyline, haloperidol, nortriptyline)	Potential increased metabolism of the psychotherapeutic agent ¹	Dosage adjustment of the psychotherapeutic agent may be needed ¹
Quinine	Potential increased metabolism of quinine ¹	Dosage adjustment of quinine may be needed ¹
Sildenafil	Potential increased sildenafil metabolism ¹	Dosage adjustment of sildenafil may be needed ¹
Sulfonylurea antidiabetic agents	Potential increased metabolism of the sulfonylurea agent ¹	Dosage adjustment of the antidiabetic agent may be needed ¹
Theophylline	Potential increased metabolism of theophylline ¹	Dosage adjustment of theophylline may be needed ¹
Tests for serum folate	Standard microbiologic assays for serum folate and	Consider using alternative

and vitamin B ₁₂	vitamin B ₁₂ are inhibited by therapeutic rifampin concentrations; similar effects may occur with rifapentine ¹	assays to determine serum folate and vitamin B ₁₂ ¹
-----------------------------	---	---

Concomitant use with HIV protease inhibitors (PIs) or certain HIV entry inhibitors not recommended unless there are no other choices because rifapentine decreases the therapeutic levels of these medications. Recent data by our group shows that it can be safely administered with efavirenz, the most commonly prescribed ART as first line therapy in Malaysia.

General Precautions

Discoloration of Body Tissues or Fluids

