Methadone: Methadone is the current standard of care for treating opioid use disorders in Malaysia, and will be provided as part of routine clinical care. The most concerning problem that we are likely to encounter is drug interactions with either TB medication (specifically rifampin) or HIV medications (for which there are many). All patients initiating TB or HIV medications AFTER being stabilized on MMT will be monitored daily for two weeks for symptoms of opioid withdrawal using the Clinical Opioid Withdrawal Scale (COWS). We anticipate, however, that most patients will start their TB medications before receiving OAT and precipitating withdrawal symptoms will be unlikely. For those already on OAT, MMT doses will be increased by 5mg per day for mild symptoms, 10 mg per day for moderate symptoms and 20 mg per day for severe withdrawal using the Clinical Opioid Withdrawal Scale (COWS).

Buprenorphine/Naloxone (BPN/NLX): BPN/NLX, also known by the name SUBOXONE, consists of a mixed medication of buprenorphine (BPN) and naloxone (NLX) in a 4:1 ratio by mass, respectively. BPN is a μ -opioid receptor partial agonist, which functions by partially activating opioid receptors and imitating its effects; however, BPN's effect plateaus, thus giving the user only a minimal effect. NLX is a μ -opioid receptor antagonist with slightly lower affinity to opioid receptors than buprenorphine. When administered in combination with BPN, it aids in further reducing the partial agonist effect of BPN, especially when such is injected. Together, they ameliorate the euphoric and sedative effects of opioids by binding and blocking opioid receptors to reduce cravings by inducing a less intense receptor activation. BPN/NLX is FDA approved to treat opioid use and alcohol use disorders, and is available for use under the tongue or on the inside of the cheek. BPN/NLX has sometimes been a preferred mode of MAT as it has a reduced potential for diversion or abuse, can be taken home for daily self-administration and has shown increased engagement and retention in community-based treatment. (Malta, et al., 2019). Additionally, The buprenorphine/naloxone combination tablet (BPN/NLX) was

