result in opiate excess. Patients are observed daily by the methadone nurse who will refer any subject noted to have excess sedation to the physician to assess dosing. Moreover, we will assess drug interaction with methadone and NNRTIs and rifampin through administration of the COWS for up to three weeks after any two medications are combined that are known to impact opiate levels. Last, we will recommend that all women use barrier contraceptives to prevent pregnancy. For women receiving MMT and who become pregnant, we will continue to monitor them and their newborn infant for adverse consequences. Any such adverse events will be reported to our IRB, and when indicated, to the drug manufacturer if a pharmacokinetic drug interaction is identified.

- d. For multi-site studies for which the Yale PI serves as the lead investigator: N/A
 - i. How will adverse events and unanticipated problems involving risks to subjects or others be reported, reviewed and managed?
 - ii. What provisions are in place for management of interim results?
 - iii. What will the multi-site process be for protocol modifications?

12. Statistical Considerations: Describe the statistical analyses that support the study design.

Analytical Plan for Aim 1

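### The methadone safety text is not consistent on when dispensing may be reduced, how sedation is detected after release, and who has COWS assessments and for how long

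*Combined protocol and SAP*

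**What the plan says.** Five places in Section V of the protocol describe how participants on methadone are supplied and watched.

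- **Item 3, Research Plan, Part C.** Methadone starts 3-4 months before release and is given daily in prison. Participants "will receive their medications weekly in form of take-way dosing", and dispensing is at the community research site. Care continues for 6 months after release, with monthly research visits that include urine testing.
- **Item 9, Risks, Methadone.** The trigger is "All patients initiating TB or HIV medications AFTER being stabilized on MMT"; these patients "will be monitored daily for two weeks for symptoms of opioid withdrawal using the Clinical Opioid Withdrawal Scale (COWS"). The section expects most patients to start TB drugs before opioid agonist treatment. For those already on such treatment, it ties methadone dose increases to COWS severity.
- **Item 10, Minimizing Risks, Monitoring Adverse Side Effects.** Methadone patients are seen daily for the first month and "may have their medications dispensed less frequently if they have no evidence of using illicit drugs", judged by self-report or urine testing.
- **Item 11, Data and Safety Monitoring Plan, Assessment of adverse consequences.** Patients on methadone who receive HIV or TB treatment are monitored for withdrawal, and also for overdose, diversion and drug interactions. No instrument or duration is given.
- **Item 11, Complications from MMT.** "Patients are observed daily by the methadone nurse who will refer any subject noted to have excess sedation"; the referral goes to the physician. Interactions of methadone with rifampin or an NNRTI are to be checked by means of "administration of the COWS for up to three weeks after any two medications are combined that are known to impact opiate levels".

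**The concern.** These places govern the same participants, and none refers to another. If staff follow different ones, withdrawal is looked for in different patients over different windows, and sedation is looked for through a contact that may not take place. Because COWS severity drives dose increases, the choice also affects how a participant is managed. The protocol requires a DSMB for Aim 1, parts a to c. That board would have difficulty reading withdrawal or sedation counts without knowing which text produced them.

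**Working it through.** The plan states no statistical figure on this point, so the check sets the texts side by side, with simple arithmetic for size.

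**1. Dispensing condition.** Take a released participant with a positive urine test for illicit drugs.

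- Under Minimizing Risks, the condition for less frequent dispensing is not met.
- Under the Research Plan, the participant receives weekly take-away doses, because no condition is stated.

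The two texts handle the same person differently. The difference in setting does not remove this: the Research Plan's take-away sentence concerns the community phase, and the Minimizing Risks condition is not confined to prison.

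**2. Detection of excess sedation.** The sentence on daily nurse observation carries no limit of setting or period, and there are two ways to read it.

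- *It covers the whole of follow-up.* Taking 6 months as 26 weeks, daily observation means 26 × 7 = 182 contacts after release. Weekly take-away gives about 26 dispensing contacts, and monthly visits give 6. The sentence cannot hold in the community phase.
- *It covers prison only.* It then agrees with daily dosing in prison, but the sedation route it describes stops at release and the text does not say what replaces it.

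Other monitoring is stated. The DSMB key elements list a weekly study meeting, daily conversations with health educators and weekly conversations with the subject, and the monitoring plan also promises overdose monitoring. None of this, in the text available, names a sedation check.

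**3. COWS.**

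| | Risks, Methadone | Monitoring plan, Complications from MMT | Monitoring plan, Assessment of adverse consequences |
|---|---|---|---|
| Trigger | TB or HIV drug started after methadone stabilisation | Two drugs known to affect opiate levels are combined; NNRTIs and rifampin named | Methadone plus HIV or TB treatment |
| Window | 2 × 7 = 14 days | up to 3 × 7 = 21 days | not stated |
| Frequency | daily | not stated | not stated |
| Instrument | COWS | COWS | not stated |

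The maximum gap in window is 21 − 14 = 7 days. The triggers also pick out different people:

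- A patient already on an interacting TB drug who then starts methadone is outside the Risks trigger. The Complications wording mentions no order of starting, so it can include this patient. The Risks section expects this order in most patients.
- A patient stabilised on methadone who starts isoniazid alone meets the Risks trigger. The Complications text does not name isoniazid, so it covers this patient only if staff count the drug as known to affect opiate levels.

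**The case against.** The strongest reply is that much of this is looseness of wording.

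- **The COWS windows can coexist.** The three-week figure is a ceiling, and two weeks of daily COWS fits under it. The Risks section does not forbid COWS in anyone else, so a site could apply each rule wherever its trigger is met. This stands. A reader might infer that no site could follow both COWS texts, or that patients who start TB drugs first are denied COWS under one of them. Neither follows, because silence is not a prohibition. What remains is that trigger, window and frequency differ and the text does not say which governs.
- **Daily and weekly contact belong to different settings.** The take-away text reads naturally as the community phase. Methadone starts 3-4 months before release, so the first month of daily contact would normally fall in prison. This also stands, and there is no conflict about prison. The post-release mismatch and the differing dispensing condition remain.
- **Safety after release is not unwatched.** A reader might infer that the safeguard against sedation and overdose disappears at release. The documents do not support that: overdose monitoring and general safety sources are stated, and part of the monitoring plan is not in the text available for review. The supported point is narrower, namely that the one sedation route described does not match the post-release contacts.
- **Rifapentine is not left out.** The interaction table lists, for rifapentine, "Potential increased metabolism of methadone", while the COWS text names rifampin. A reader might infer a gap, but both triggers are broad enough to include rifapentine.
- **No endpoint depends on this.** Part C's primary outcome is TB treatment completion, and neither COWS nor sedation is an endpoint. This stands and limits the point to safety ascertainment and management.

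**Conclusion.** The methadone safety text needs reconciling on three matters: the condition for less frequent dispensing, the statement of how sedation is detected once participants leave prison, and the COWS trigger, window and frequency. The first is a direct difference in handling. The second is a statement that either cannot hold after release or does not apply there. The third is an unreconciled set of rules, not a pair of incompatible numbers.

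Dispensing and sedation bear on the methadone arm, anticipated at 25-50 participants. A reader might extend the COWS point to all of them, but Part C admits people with no TB, and someone taking neither TB nor HIV drugs need not meet any trigger. The number affected for COWS cannot be derived from the documents. The 182 against 26 comparison holds only if the daily-observation sentence is read to cover the community phase and 6 months is taken as 26 weeks.

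No efficacy endpoint, analysis or sample size changes. The conclusion about sedation rests on the monitoring text available, so any sedation check in the unavailable part would narrow it further.

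**What to change.** The sponsor's clinicians should reconcile the Part C Research Plan, the Methadone paragraph under Risks, Monitoring Adverse Side Effects under Minimizing Risks, and the two items of the monitoring plan, so that the protocol contains:

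- one COWS rule, with trigger, window and frequency given once and cross-referenced elsewhere;
- one statement of the condition under which methadone is dispensed less often, including how it applies after release;
- a sedation sentence that describes the contacts that will actually occur, separately for prison and for the community phase.

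The choice of trigger, window and dispensing condition is a clinical decision and is not proposed here. Reporting withdrawal and sedation events separately for the two settings would help the DSMB, but is optional.

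The cost is protocol wording and matching changes to the forms. Any extra assessments would come from the clinical rule chosen, since the reconciliation itself adds none.
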